### 2.4.4. Safety Analyses

The safety will also be assessed by the analysis of secondary procedures and adverse events.

#### 2.4.4.1. Secondary procedures

- Secondary procedure rate and reasons
- Endovascular/surgical treatment details
- Imaging abnormalities

#### 2.4.4.2. Adverse events

The adverse events analysis will present the number of event of each following category, the number of patients with at least one event of each category and the corresponding percentage:

- Adverse events (overall, serious, device-related and procedure-related)
- Reasons of SAE seriousness.

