The benchmark treatment differs, depending on whether it is a type A dissection (ascending aorta origin) or a type B dissection (descending aorta origin). Type A dissections require emergency surgical treatment. For uncomplicated type B dissections, antihypertensive medical treatment is the benchmark treatment. In the event of complications, surgery is indicated. Contraindications to surgical treatment are mainly related to older patient age and cardiorespiratory issues. Acute hemiplegia or mesenteric infarction of more than 6 hours are also contra-indications for surgery². In the acute phase, mortality rates for surgical treatment range between 20 and 35% and medullary complications between 10 and 20%.

Aortic isthmus ruptures and penetrating ulcers:

In the event of trauma to the thoracic aorta, the use of a thoracic aortic endoprosthesis can be especially useful for patients with multiple traumas who are often not candidates for open surgery. Their lesions can be treated with the GORE® TAG® and Conformable GORE® TAG® Thoracic Endoprostheses as a substitute for surgical treatment.

However, the data on the long-term outcome of such endoprostheses has been deemed as inadequate by the French National Health Authority (HAS). This has caused the HAS to subject any renewal for inclusion on the list of reimbursable products and services (LPPR) to the implementation of an observational follow-up study on a cohort of patients representative of the population treated under real-life conditions, with a 5-year follow-up.

[figure not shown]

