#### CONFIDENTIEL / CONFIDENTIAL

## STATISTICAL ANALYSIS PLAN

They will be presented as categorical variables (with the corresponding 95% bilateral CI) by time-point and described over time by a survival curve as per the Kaplan-Meier method together with the associated estimators.

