## CONFIDENTIEL / CONFIDENTIAL

## STATISTICAL ANALYSIS PLAN

- Derived criterion "exclusion of the false lumen without endoleak" will be defined as follows:  
"Exclusion of the main entry of the dissection" will be YES if:
  - no false lumen perfusion type Ia, Ib, III is ticked
  - and "Incorrect Deployment" is not ticked or "false lumen perfusion through a tear proximal to the device in an untreated segment (not an endoleak)" is not ticked
  - and "Status of false lumen located opposite the treated part of the aorta" is "Complete thrombosis"
 If the perfusion status is unknown or if the false lumen thrombosis status is unknown then "exclusion of the false lumen without endoleak" will be missing.
- Derived criterion "exclusion of the penetrating aortic ulcer without endoleak" will be defined as follows:  
No maximum aortic diameter of the ulcer increase > 5 mm (compared to 1st post-op exam) and no type I or type III endoleak
- Derived criterion "exclusion of the rupture site without endoleak" will be defined as follows:  
No type I or type III endoleak
- Mortality from thoracic disease is defined as any death occurring as a result of complication of aortic disease (rupture, conversion, etc.) or following any surgery intended to treat the aortic disease. It will be derived as follows:
  - If the death occurs within 30 days after the initial procedure or any re-intervention or
  - If the death is related to the disease
 Then mortality from thoracic disease will be "YES"
- An adverse event (or any other parameter that is not reported in a follow-up CRF) will be considered as having occurred
  - "at 1 month" if it occurs between the procedure (included) and 30 days after the procedure
  - "at 1 year" if it occurs between the procedure (included) and 365 days after the procedure
  - "at 2 year" if it occurs between the procedure (included) and 731 days after the procedure
  - "at 3 year" if it occurs between the procedure (included) and 1096 days after the procedure
  - "at 4 year" if it occurs between the procedure (included) and 1461 days after the procedure
  - "at 5 year" if it occurs between the procedure (included) and 1826 days after the procedure

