### Adverse events

Table 66: Adverse events (Type 8)

Table 67: Reasons of SAE seriousness (Type 6)

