### 5.3.1. Adverse events (Type 8)

Adverse events	Population (N=XX)		
	NAE (1)	n (2)	% (3)
ALL	XX	XX	XX.X
Type 1	XX	XX	XX.X
Type 2	XX	XX	XX.X
...	...	...	...
Type n	XX	XX	XX.X

[figure not shown]
(1): Number of adverse events/medication of a given type of adverse event/medication

(2): Number of patients with at least one adverse event of a given type of adverse event

(3): (n / N)\*100 (N: total number of patients)

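### Table 66 gives pooled adverse events without timing, so operative and late events cannot be separated for the few categories that no other planned output covers

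*SAP*

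**What the plan says.** SAP 2.4.4.2 asks, for each of four categories (overall, serious, device-related, procedure-related), for the number of events and for "the number of patients with at least one event of each category and the corresponding percentage". The output list in SAP 4.1 assigns this to Table 66, layout Type 8. Unlike Tables 46 to 59, Table 66 carries no time-point label. The Type 8 shell (SAP 5.3.1, Adverse events) has three columns: event count (NAE), patients affected (n) and percentage. Its footnote fixes the denominator: "N: total number of patients". Table 67, on reasons for seriousness, has no time-point label either.

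SAP 2.5 does define timing rules. They open with "An adverse event (or any other parameter that is not reported in a follow-up CRF) will be considered as having occurred" and then set windows ending at day 30 and at years 1 to 5. Each window starts at the procedure; the last applies "if it occurs between the procedure (included) and 1826 days after the procedure". The windows are therefore cumulative.

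The complication endpoints are treated differently. Under SAP 2.4.3.2 they are shown "by time-point and described over time by a survival curve as per the Kaplan-Meier method together with the associated estimators".

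**The concern.** The study was requested because, in the words of Protocol 1.1, "the data on the long-term outcome of such endoprostheses has been deemed as inadequate". Its objective includes safety at 5 years (SAP 1.1). A single percentage running from the procedure to the end of follow-up mixes two risks: that of the operation, concentrated in the first month, and that of living with the device. A patient with an operative event and a patient whose first event comes in year 4 count alike.

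The denominator also ignores how long each patient has been observed. The Protocol Summary promises the health authority a report each year, and SAP 2.4.1 foresees intermediary reports. A percentage of this kind will rise from one report to the next even if risk is constant. A reader of Table 66 alone could not tell a late problem from accumulating follow-up.

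**Working it through.** The documents state no adverse-event rate, so there is no plan figure to reproduce. The check has two parts: what is already timed elsewhere, and what Table 66 can and cannot distinguish.

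**1. Coverage (SAP 4.1 and 4.2 against Protocol 5.3)**

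| Event | Time-point table | Kaplan-Meier |
|---|---|---|
| All-cause death | 46-48 | Graphs 1-3 |
| Neurological complications | 54 | Graph 4 |
| Cardiac, renal, pulmonary complications | 55 | Graph 5 |
| Device-related complications | 56 | Graph 6 |
| Surgical conversion | 57 | Graph 7 |
| Secondary procedures | 58 | Graph 8 |
| Disease-related death | 59 | Graph 9 |
| Overall, serious, procedure-related events (pooled) | none | none |
| Vascular, visceral, infectious complications, unless classed as device-related | none | none |

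Only the last two rows lack a timed summary. Some events in them are timed indirectly, for example when they lead to a secondary procedure or death.

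**2. Same entry from different timing.** N = 160 is from the documents; the splits are assumed. Let first events occur in 35, 30, 25, 20 or 5% of patients by day 30, and in a further 0, 5, 10, 15 or 30% later. Each sum is 35%, so n = 0.35 × 160 = 56. Table 66 shows 56/160 = 35.0% every time (exact 95% CI 27.6 to 42.9). A day-30 column would show 35, 30, 25, 20 or 5%.

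**3. Illustration with hazards (all rates assumed).** Let e be the early risk, h the late event hazard per year, m = 0.05 the later death hazard, and 0.92 the share surviving the operative period, taken as independent of early events for simplicity. Then T = 5 − 30/365.25 = 4.918 years, and

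- L = h/(h+m) × [1 − exp(−(h+m)T)], the late risk among patients alive after day 30
- n/N = e + (1−e) × 0.92 × L

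Cohort A (e = 0.20, h = 0.12): L = 0.7059 × (1 − 0.4334) = 0.400; n/N = 0.20 + 0.80 × 0.92 × 0.400 = 49.4%.

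Cohort B (e = 0.40, h = 0.04): L = 0.4444 × (1 − 0.6424) = 0.159; n/N = 0.40 + 0.60 × 0.92 × 0.159 = 48.8%.

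The totals differ by less than one point; the late risks are 40.0% and 15.9%. The pairing was chosen so that the totals come close. It shows what can happen, not what is likely.

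**4. Rise between reports (same assumptions, e = 0.30, h = 0.08).** Entry is uniform over 24 months and early events are spread evenly over 30 days (0.0821 years). At month 12, follow-up is uniform from 0 to 1 year:

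- early part: 0.30 × (1 − 0.0821/2) = 0.2877
- late part: 0.70 × 0.92 × 0.6154 × [0.9179 − (1 − exp(−0.13 × 0.9179))/0.13] = 0.0209
- total: 30.9%

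At month 84 everyone has complete follow-up: L = 0.6154 × (1 − 0.5277) = 0.2907, and n/N = 0.30 + 0.70 × 0.92 × 0.2907 = 48.7%. Risk is unchanged throughout.

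**5. Unequal follow-up (assumed annual exit of 5 to 15%).** For a late event rate of 2% per year, crude n/N over 5 years is 8.5% down to 6.6%, against 9.6% for one minus Kaplan-Meier. For 5% per year it is 20.1% down to 15.8%, against 22.6%. The gap is a shortfall only insofar as exit means loss to follow-up. Where exit is death, n/N is the proportion of patients actually affected.

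**The case against.** The strongest reply is that Table 66 is supplementary. SAP 2.4.4 says safety will also be assessed this way, after the endpoints have been analysed. A reader might infer from Table 66 that the long-term safety signal cannot be seen. The documents do not support that: the outputs in the first seven rows of the coverage table carry it, and they are the protocol's own endpoints. Protocol 5.3 lists pulmonary, neurological, cardiac and renal complications among the serious events, so much of the serious category is timed under other names. The SAP 2.5 windows plausibly serve those endpoint tables and are not idle.

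A reader might also infer that a late event following an early one disappears. It does not. NAE counts it; only n and the percentage count a patient once. In addition, Listing 25 lists the adverse events, SAP 2.4.1 reports follow-up duration in intermediary reports, and a single incidence table is a common choice in a single-arm registry.

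All of this stands, and it limits the point. It does not remove it. NAE is untimed as well, a listing is not a summary, and follow-up duration shown elsewhere does not let a reader divide Table 66 into early and late events.

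**Conclusion.** The point holds in a limited form and is minor to moderate. Table 66 cannot separate operative from late events. This matters for pooled overall, serious and procedure-related events and for vascular, visceral and infectious complications not classed as device-related, because no other planned table or curve gives their timing. A late infection judged unrelated to the device, and leading to neither re-intervention nor death, would enter the summaries only through an untimed table.

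The reading of the layout rests on the text alone. The sizes in steps 2 to 5 rest on assumed rates and are illustrative. They show that early and late risk can offset each other in the total and that the percentage must grow with follow-up. They do not show that operative events will dominate in this cohort, or that the study's objective is defeated.

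**What to change.** Change SAP 2.4.4.2 and the Table 66 shell as follows.

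- Present the four categories by the windows of SAP 2.5, with NAE, n and percentage in each. Add rows for vascular, visceral and infectious complications.
- Because those windows all start at the procedure, add two separate intervals: day 0-30 and after day 30. For the late interval, give the number of patients alive and under follow-up at day 31 and the event count NAE, so that a late event after an early one is visible. Events per 100 patient-years are optional.
- In intermediary reports, state how many patients have been followed to the end of each window, so that an incomplete window is recognisable.
- Keep the present total as the last column.

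The cost is SAP wording, one longer table and small counts in the late period. No new data are needed, since Protocol 5.3 already collects the date of each event.

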## 2.5. Derived Criteria Calculation

- A patient will be considered as fulfilling the eligibility criteria if:
  - Inclusion criterion 1 is ticked YES
  - Inclusion criterion 2 is ticked YES or date of informed consent is filled
  - Inclusion criterion 3 is ticked YES
  - Exclusion criterion 1 is ticked NO
  - Exclusion criterion 2 is ticked NO
- Total study duration will be calculated as:  
Total study duration = study exit date - procedure date +1  
If the procedure date is not available, the baseline date will be used instead.
- Study follow-up duration will be calculated as:  
Study follow-up duration = last FUP date available - procedure date +1  
If the procedure date is not available, the baseline will be used instead.  
If the visit date is not available, the corresponding last imaging date will be used instead.
- Body Mass Index will be calculated as:  
 $BMI = \text{weight (kg)} / (\text{height (m)})^2$
- Derived criterion “life-threatening emergency” will be derived as follows:
  - if vital urgency specify is “Aortic rupture” then life-threatening emergency will be “Yes: Aortic rupture”
  - else if vital urgency specify is “Dissection complicated by malperfusion” then life-threatening emergency will be “Yes: Dissection complicated by malperfusion”
  - else if vital urgency specify is “Other” then life-threatening emergency will be “Yes: Other”
  - else if vital urgency is “No” then life-threatening emergency will be “No”
- Derived criterion “procedure duration” will be calculated as follows:  
Procedure duration = procedure end time – procedure start time
- Derived criterion “exclusion of the aneurysm without endoleak” will be defined as follows:  
No maximum diameter of the aneurysm sac increase > 5 mm (compared to 1st post-op exam) and no type I or type III endoleak

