2.2.2 Secondary endpoint criteria

The secondary endpoints assessing the usefulness of the technique at different follow-up visits (after surgery or in the months following the surgery, at 1 year, 2 years, 3 years, 4 years and 5 years) will be:

- The exclusion rate of aneurysm, of penetrating aortic ulcer, of false lumen or site of rupture, with no endoleak, as defined above
- The rate of neurological complications
- The rate of cardiac, renal and pulmonary complications
- The rate of device-related complications
- The rate of surgical conversion
- The rate of secondary procedures
- The rate of mortality related to the disease

Definitions:

- Migration: movement evaluated on a workstation with 3D reconstruction according to the reference examination (1st post-op imaging examination)
 - Proximal movement > 10 mm or ≤ 10 mm with coverage of a branch of the supra-aortic trunks
 - Distal movement > 10 mm or ≤ 10 mm with coverage of the celiac trunk
- Exclusion of the aneurysm:
 - No type I or type III endoleak associated with the lack of increase in the maximum diameter of the aneurysm sac > 5 mm (reference examination 1st post-operative examination)
- Exclusion of the penetrating ulcer:
 - No type I or type III endoleak associated with the lack of increase in the maximum aortic diameter compared to the ulcer > 5 mm (reference examination 1st post-operative examination)
- Exclusion of rupture site:
 - No type I or type III endoleak
- Exclusion of the false lumen (dissection):
 - Exclusion of the main entry of the dissection
 - Thrombosis of the false lumen at the endoprosthesis
- Mortality from thoracic disease is defined as any death occurring as a result of complication of aortic disease (rupture, conversion, etc.) or following any surgery intended to treat the aortic disease.

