5.4 End of patient participation

5.4.1 Procedure to withdraw from the study

The withdrawal procedure from the study applies when patient data are no longer collected. Discontinuation of patient data collection will occur in the following cases:

- The patient decides to withdraw from the study at any time, for whatever reason, without having to justify such a decision
- Decision made by the doctor to stop the patient's participation in the study in order to protect the patient's well-being
- Patient lost to follow-up
 - Note: the patient may not be considered as being lost to follow-up by the investigator as long as the follow-up period (5 years) has not elapsed.
- Patient's death
- Normal end of the observational study

Data on patients, for whom the study endoprosthesis was introduced at the arterial access but not inserted during the initial intervention (failed installation), will be collected until the patient's withdrawal. Thereafter, a withdrawal form from the observational study must be completed.

Patients for whom the endoprosthesis will be explanted during the follow-up period should be evaluated clinically at least until the last 5-year visit.

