#### 2.4.3.2. Secondary Analyses

The secondary endpoints for assessing the usefulness of the technique will be:

- The exclusion rate of the aneurysm, the false lumen, the penetrating aortic ulcer or rupture site, with no type I or III endoleak (overall and by main indication for implantation)

It will be presented as categorical variables (with the corresponding 95% bilateral CI) by time-point, starting at 30 days.

- The rate of neurological complications
- The rate of cardiac, renal and pulmonary complications
- The rate of device-related complications
- The rate of surgical conversion
- The rate of secondary procedures (re-interventions)
- The rate of mortality related to the disease

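### The SAP 2.5 exclusion rules have no failure clause for conversion, explantation or failed deployment, so these patients can score as excluded or leave the denominator, and either raises the rate

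*SAP*

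**What the plan says.** Exclusion of the lesion is a secondary endpoint. It is reported as a percentage with a 95% confidence interval at each time point from 30 days (SAP 2.4.3.2, Tables 49-53). SAP 2.5 derives it by lesion type:

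- Aneurysm: "No maximum diameter of the aneurysm sac increase > 5 mm" relative to the first post-operative examination, and no type I or III endoleak.
- Penetrating ulcer: "No maximum aortic diameter of the ulcer increase > 5 mm" against the same reference, and "no type I or type III endoleak".
- Rupture site: absence of type I or III endoleak only. Protocol 2.2.2 has the same content: "No type I or type III endoleak".
- False lumen: no perfusion of the listed types, a condition on two imaging items, and complete thrombosis recorded under "Status of false lumen located opposite the treated part of the aorta". A sentence beginning "If the perfusion status is unknown or if the false lumen thrombosis status is unknown then" makes the result missing when either status is unknown.

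Four other provisions decide who enters these percentages:

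- Protocol 3.1 enrols patients whether or not the implant succeeded, and the PP set in SAP 2.3.1 requires only that the device was introduced.
- Protocol 5.4.1 collects data on failed installations until withdrawal. For explanted devices it says: "Patients for whom the endoprosthesis will be explanted during the follow-up period should be evaluated clinically at least until the last 5-year visit". That sentence does not mention imaging.
- SAP 2.1.1 takes percentages over non-missing observations, and SAP 2.1.3 replaces no missing values.
- Conversion is a separate endpoint, "The rate of surgical conversion" (SAP 2.4.3.2, Table 57 and Graph 7). Deployment failure is in Table 31. Neither enters the exclusion derivation.

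**The concern.** Three of the four rules are met by the absence of adverse findings, with no condition that the endoprosthesis is in place. A patient with no endograft in the aorta cannot show an endoleak. After open replacement there may also be no sac left to grow. The patients in whom the device most clearly did not do its job can therefore satisfy the rule, or have no imaging and disappear from the percentage.

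The study objective is the efficacy and safety of this endoprosthesis at 5 years, and a report goes to the health authority each year. An exclusion rate that stays level or rises when a graft is removed is hard to interpret for that purpose. Without a written rule, the classification falls to whoever completes the imaging page or programs the table.

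**Working it through.** The visible text states no expected exclusion rate or conversion rate and no precision target for this endpoint, so there is no planned figure to reproduce. The check has two parts.

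**1. Literal application of the SAP 2.5 rules**

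| Case | Result |
|---|---|
| Aneurysm, explanted, sac replaced, no endoleak | excluded |
| Aneurysm, not deployed, growth 3 mm, no endoleak | excluded |
| Aneurysm, not deployed, growth 8 mm | failure |
| Aneurysm, no imaging | missing |
| Rupture site, explanted or not deployed, no endoleak recorded | excluded |
| Rupture site, no imaging | missing |
| False lumen, not deployed, patent or partly thrombosed | failure |
| False lumen, not deployed, status unknown | missing |

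The ulcer rule behaves like the aneurysm rule. The false-lumen rule is stricter because complete thrombosis must be recorded. It does mention incorrect deployment, but joins that item by *or* to the proximal-tear item. Ticking incorrect deployment alone, with complete thrombosis, therefore still gives excluded. Loss of the device is never in itself a failure, although failure can be reached by other routes.

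**2. Size**

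All inputs here are assumptions: 75 other patients imaged at 5 years, 88% of them excluded (66 of 75), and c = 2, 5 or 8 patients converted, explanted or not deployed.

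- Scored as success: (66 + c)/(75 + c)
- Missing: 66/75 = 88.0%
- Counted as failure: 66/(75 + c)

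| c | Success | Missing | Failure | Shift if success | Shift if missing |
|---|---|---|---|---|---|
| 2 | 68/77 = 88.3% | 88.0% | 66/77 = 85.7% | 2/77 = 2.6 points | 2.3 points |
| 5 | 71/80 = 88.75% | 88.0% | 66/80 = 82.5% | 5/80 = 6.25 points | 5.5 points |
| 8 | 74/83 = 89.2% | 88.0% | 66/83 = 79.5% | 8/83 = 9.6 points | 8.5 points |

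A second set of assumptions uses the full 160 patients, with 3, 8 or 16 such patients and 80%, 90% or 95% exclusion in the rest. It gives upward shifts of 1.5 to 1.9, 4.0 to 5.0 and 8.0 to 10.0 points. The lower end of each range is for missing and the upper end for success. For scale, with 8 such patients and 90% in the others, the rate with failures counted is 137/160 = 85.6% (exact 95% CI 79.2 to 90.7). It is 137/152 = 90.1% if they are missing and 145/160 = 90.6% if they score as success.

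**The case against.** The strongest reply concerns the endpoint itself. The aneurysm, ulcer and rupture-site rules follow Protocol 2.2.2, which describes the state of the lesion at a time point and treats conversion and re-intervention as separate endpoints. The documents do not say that loss of the device must count as failed exclusion. This stands in part. The upward shift is measured against a definition that the plan does not state, and changing the definition needs a matching note in the protocol. But a patient with no endograft in place can hardly show that the endoprosthesis excluded the lesion, and the plan leaves that case unaddressed.

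A reader might go further and infer that the rules can never return failure for these patients. They can: growth over 5 mm fails under the aneurysm and ulcer rules, a false lumen not completely thrombosed fails, and a patient converted because of endoleak or growth fails at earlier visits where that was imaged.

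A reader might also infer that every converted patient scores as success. The documents do not establish this. Explanted patients are to be followed clinically, with imaging unmentioned. Conversion appears on the study-exit form as well as the re-intervention form (Protocol 5.2, SAP 1.3.4). The final eCRF, which would show how the imaging page is completed after explantation, is not among the documents. Missing is at least as plausible as success, which is why both are shown.

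Nor are these events hidden. Tables 31, 57, 58 and 60-65 report deployment failure, conversion and secondary procedures, including endoleak details afterwards. What they do not do is alter Tables 49-53.

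Finally, coding failure at every later time point without limit would keep these patients in the denominator after death or exit, while others who die or leave become missing. That would bias the rate downward. The objection is sound, and the fix has to be limited accordingly.

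**Conclusion.** The gap is real, and it is more than missing detail, because the stated rules applied as written give a misleading result. No exclusion rule treats conversion, explantation or failed deployment as failure. Under the aneurysm, ulcer and rupture-site rules such a patient is scored as excluded or drops out, and both raise the rate relative to counting device loss as failure. The size cannot be derived from the documents. Under the assumptions of 75 other imaged patients at 88% and 2 to 8 such patients, the shift is about 2.6 to 9.6 points if they are scored as success and 2.3 to 8.5 points if they are missing. With very few such patients the effect is small. This is a descriptive secondary endpoint in a single-arm registry with no visible threshold, and the primary mortality endpoint is unaffected. The change should still be made, because the rate is reported to the health authority and the correction is cheap.

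**What to change.** Add to SAP 2.5:

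> For a patient still alive and in follow-up at a time point, exclusion is NO if surgical conversion or explantation occurred on or before that time point, or if the device was not deployed at the index procedure. A failed deployment is counted NO at the 30-day time point if the patient is alive at that time point, even if the patient exits early.

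Apply this to Tables 49-53 and show the rate under the current rule as a sensitivity row. The limit to patients alive and in follow-up keeps death and exit handled as for everyone else. The 30-day provision stops failed deployments from vanishing through early exit before they are ever counted.

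The cost is one clause, one extra row per table and a matching note to the definitions in Protocol 2.2.2. The implantation, re-intervention and study-exit forms already cover these events, so no new data or procedures are needed. The downside is a slightly less favourable exclusion rate. Separate rows for exclusion with and without prior re-intervention are optional.

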5 CONDUCTING THE OBSERVATIONAL STUDY

5.1 Schedule of visits

The schedule and procedures for monitoring the patients included in this study adhere to the recommendations of the French National Health Authority², namely annual monitoring by CT scan or MRI + X-ray for 5 years.

During this observational study, there will be no requirement for any specific examination or procedure outside the scope of practice of each center.

The monitoring schedule and procedures may be alleviated based on future recommendations.

Monitoring schedule and procedures recommended by the French National Health Authority:

	Post-operative follow-up (D1 to D30)	Follow-up at 1 year	Follow-up at 2 years	Follow-up at 3 years	Follow-up at 4 years	Follow-up at 5 years
Clinical evaluation	X	X	X	X	X	X
CT scan or MRI + X-ray	X	X	X	X	X	X

Note: Centers are requested to adhere to the visit schedule to the best of their ability. This adherence to schedule is essential for a scientific analysis of results. However, some centers may follow a different follow-up protocol (different intervals, less invasive tests such as Echo-Doppler) if no anomaly was found in the previous examination.

Investigators are requested to limit the number of patients lost to follow-up insofar as possible. If a patient misses a clinical and/or radiological follow-up, the investigator is asked to contact the patient by all possible means in order to optimize data collection. At each clinical assessment, the investigator must interview the patient (neurological, cardiac, renal and pulmonary exams) and ensure that the patient has not had any surgery since the last assessment.

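### For aneurysm and ulcer patients, the growth part of exclusion is met automatically at the visit that supplies the first post-operative exam, so the 30-day figure can be endoleak status alone

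*SAP*

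**What the plan says.** SAP 2.5 defines aneurysm exclusion as "No maximum diameter of the aneurysm sac increase > 5 mm (compared to 1 st post-op exam", together with the absence of a type I or III endoleak. The ulcer rule in the same section is "No maximum aortic diameter of the ulcer increase > 5 mm (compared to 1 st post-op exam) and no type I or type III endoleak". Protocol 2.2.2 names the same comparator for both: "reference examination 1st post-operative examination". None of these places gives the reference exam a time window, requires the scored exam to come after it, or says how to code growth when no earlier post-operative exam exists.

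SAP 2.4.3.2 presents the exclusion rate "by time-point, starting at 30 days". It appears by time-point in Table 49 (pooled), Table 50 (aneurysm) and Table 52 (ulcer). Protocol 5.1 schedules one imaging assessment between D1 and D30 and then one a year to year 5, but states that "there will be no requirement for any specific examination or procedure outside the scope of practice of each center".

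Two other provisions bear on the point. Protocol Table 2 and the flowchart in SAP 1.3.4 tick imaging tests on the post-operative form, which covers surgery to discharge, as well as on the follow-up form. For the false lumen, SAP 2.5 sets exclusion to missing when perfusion or thrombosis status is unknown. It has no matching sentence for the aneurysm or the ulcer.

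**The concern.** A growth criterion needs two exams. If the first post-operative exam is also the exam being scored, the difference is zero whatever the sac or ulcer is doing. A component that could not be assessed is then counted as met, and the patient is a success if there is no type I or III endoleak.

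Two things are at stake. First, the 30-day column may hold a different endpoint (endoleak only) from the 1- to 5-year columns of the same tables, so a reader following the row over time would not be comparing like with like. Second, where the self-comparison happens at a later visit, the reported rate at that visit can only be too high. Exclusion is the first-listed secondary endpoint, in a study whose data the protocol says will be required for renewal of the device's registration.

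**Working it through.** The documents give no exclusion, growth, endoleak or late-imaging rate, so there is no planned figure to reproduce. The check is a reading of the rule followed by an illustration.

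**Applying the rule**

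1. *30 days, with the D1-D30 exam the first after surgery.* Reference and scored exam are the same. Growth is 0 mm, the growth part passes in 100% of such patients, and the composite equals the proportion without a type I/III endoleak.
2. *30 days, with a pre-discharge scan on record.* The reference is earlier and the comparison is genuine.
3. *First exam at 1 year.* Growth at 1 year is again 0 mm by construction. From year 2 the comparison is real but starts from the 1-year diameter.
4. *Direction of a late reference.* A sac that grows 4 mm in year 1 and 4 mm afterwards has grown 8 mm. It fails against an early reference and passes against a 1-year reference (4 mm). A sac that shrinks 6 mm by year 1 and regrows 6 mm passes against an early reference (net 0 mm) and fails against a 1-year reference (+6 mm). A late reference can err either way; only the self-comparison is one-directional.

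**Illustrative size at an affected visit**

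Assumptions, none of them in the documents: e = probability of type I/III endoleak (5 to 10%); g = probability of true growth above 5 mm (5 to 15%); f = share of patients whose first exam is the one being scored (5 to 30%); growth and endoleak independent.

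- Rate under the rule as written: (1−e) × [(1−f)(1−g) + f]
- Rate with a valid earlier reference: (1−e)(1−g)
- Upward bias: (1−e) × f × g

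With e = 5%, g = 10%, f = 10%: as written 0.95 × (0.90 × 0.90 + 0.10) = 86.45%; valid reference 0.95 × 0.90 = 85.5%; bias 0.95 points.

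Low end (e = 10%, g = 5%, f = 5%): 0.90 × 0.05 × 0.05, about 0.2 points. High end (e = 5%, g = 15%, f = 30%): 0.95 × 0.30 × 0.15, about 4.3 points. At 30 days with f = 1, the reported rate is 1−e: 95% for e = 5% and 90% for e = 10%.

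For scale, the 95% Wald half-width, 1.96 × √[p(1−p)/n], at p = 85 to 90% is 5.9 to 7.0 points for n = 100 and 8.3 to 9.9 points for n = 50. These subgroup sizes are assumed: the documents give 160 patients across all indications and no split.

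**Why the composite should be missing even when an endoleak is seen**

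If non-assessable patients counted as failures with an endoleak and as missing without one, the rate would be (1−f)(1−e)(1−g) / [(1−f) + f×e]. With e = 5%, g = 10%, f = 10% this is 0.7695 / 0.905 = 85.0%, below the valid 85.5%. At f = 1 it is 0%, because only failures would remain. Setting the composite to missing for all such patients gives 85.5%, provided that late imaging is unrelated to growth.

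**The case against.** A reader might infer that the exclusion rate itself passes automatically. It does not: both rules also require no type I or III endoleak, and that part can fail at every visit. The rupture-site and false-lumen rules have no growth part, so only aneurysm and ulcer patients, and the pooled rate through them, are affected.

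A reader might also infer that every 30-day result is a self-comparison, or that the error always favours the device. Neither is supported. The post-operative form can supply an earlier scan, and a late reference can bias later visits in either direction.

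Nor do the documents show late first imaging to be common. Protocol 5.1 asks centers to keep to the schedule, and its allowance for different intervals depends on a previous exam without anomaly, so it presupposes an early exam. A late first exam is possible only because imaging is not compulsory.

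The best defence of the text is that it never says an exam is compared with itself. SAP 2.1.3 replaces no missing data, SAP 2.1.1 bases percentages on non-missing observations, and the Type 4 table layout shows missing counts. A programmer could code growth as missing without contradicting the plan. But nothing tells the programmer to do so. The diameter at the scored visit is present, so the missing-data rule is not triggered, and applying the criterion literally returns no growth. The SAP supplies an explicit missing rule for the false lumen and not here. The objection narrows the point without removing it.

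**Conclusion.** The point holds for the growth component in aneurysm and ulcer patients, at whichever visit supplies the first post-operative exam. It follows from the wording of the rule and needs no assumption about rates. For patients without a pre-discharge scan, the 30-day exclusion figure in Tables 49, 50 and 52 is endoleak status only.

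How many patients this concerns, and by how much any later rate moves, cannot be derived from the documents. The range of about 0.2 to 4.3 points rests wholly on the assumed inputs and is smaller than the likely confidence-interval half-width. The endpoint is secondary and descriptive, with no test attached, and the documents do not support reading the point as a threat to the primary mortality result. It is still worth correcting, because the self-comparison runs in one direction and the correction is cheap.

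**What to change.** In SAP 2.5, with matching text in Protocol 2.2.2:

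- Evaluate growth only on an exam dated after the reference exam.
- Where no earlier post-operative reference exists, set the composite exclusion criterion to missing whatever the endoleak status, as is already done for unknown false-lumen status, and report type I/III endoleak separately.
- In the 30-day column of Tables 49, 50 and 52, label the result for these patients *no type I/III endoleak (growth not assessable)*, kept apart from the composite.
- Show the number not assessable at each time-point.
- State an early window for the reference exam, with a reasonable tolerance beyond D30. Flag patients whose reference falls outside it and run a sensitivity analysis without them. Do not discard them from the main analysis: a strict D30 cut-off would make a patient with a day-35 reference not assessable at every annual visit.

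The cost is SAP and protocol wording and a few lines of programming. It needs no new imaging and changes no patient care. The price is more missing values, above all at 30 days where the composite may be available for few patients, and possibly a slightly less favourable exclusion rate.
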